15.5 Pupil Diameter

Pupil diameter will be measured in mm pre- and post-treatment at Visit 1 and post-CAE® at Visit 2. The observed and change from baseline pupil diameter will be summarized for each eye (study eye and fellow eye) using continuous descriptive statistics by visit for each treatment group. A subject listing of pupil diameter will also be produced.

16. Other Analyses

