 - Treatment with Investigational drug/placebo will be administered upon participant reporting an Ocular Discomfort score ≥ 3 at two or more consecutive time points in at least one eye during CAE® exposure (if a participant has an Ocular Discomfort rating of 3 at time = 0 for an eye, s/he must report an Ocular Discomfort rating of 4 for two consecutive measurements for that eye) using the ██████████ Scale. Participant will resume symptom assessments 1 minute after the application ends every 5 minutes.
- BCVA
- Slit lamp biomicroscopy

- Intranasal Examination
- Urine Pregnancy Test (if applicable)
- Concomitant Medications
- AE Query
- Study exit

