8.3 Safety

The Safety population includes all randomized subjects who have received at least one dose of the investigational product. Subjects in the Safety population will be analyzed as treated.

9. General Statistical Considerations

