14.1.2 EYE DRYNESS SCORE AS THE PRIMARY ANALYSIS

Eye dryness will be assessed pre-treatment at Visit 1, pre-CAE at Visit 2, and every 5 minutes during CAE® exposure at Visit 2. For each assessment, the participant will be asked to rate their ocular symptoms (both eyes simultaneously) due to eye dryness by placing a vertical mark on a 100 mm horizontal line to indicate the level of discomfort; 0 corresponds to "no discomfort" and 100 corresponds to "maximal discomfort".

Treatment with study drug will be administered upon the participant reporting an Ocular Discomfort ([REDACTED] Scale) score ≥ 3 at two or more consecutive timepoints in at least one eye during CAE® exposure. If a participant has an Ocular Discomfort rating of 3 at time = 0 for an eye, s/he must report an Ocular Discomfort rating of 4 for two consecutive measurements for that eye. Participant will resume symptom assessments 1 minute after the application ends every five minutes.

The primary analysis will be a one-timepoint analysis in which the pre-treatment EDS will be the EDS at the timepoint that the subject first qualifies for study drug administration during the CAE® and post-treatment EDS will be the EDS at the first timepoint following qualification. If a participant fails to qualify

for study drug administration, the timepoint of qualification and the pre-treatment and post-treatment EDS will be missing.

Eye dryness score will be summarized by visit, timepoint, and treatment with quantitative descriptive statistics (n, mean, median, standard deviation, minimum and maximum).

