[REDACTED] Ocular Discomfort Scale results will be summarized by timepoint at Visit 2 and treatment with quantitative descriptive statistics. Change from pre- to post-treatment in [REDACTED] Ocular Discomfort Scale results will also be summarized by timepoint (based on the timepoint from the pre-treatment assessment to the respective post-treatment assessment) at Visit 2 and treatment group with quantitative descriptive statistics in a manner similar to EDS. [REDACTED] models will be used that include pre-treatment ocular discomfort, timepoint of qualification, treatment and study site as covariates. [REDACTED] analysis estimates of pre- to post-treatment changes will be displayed graphically by timepoint

in a line plot by treatment group. Two sample t-tests and non-parametric Wilcoxon rank sum tests will be used to compare treatments as unadjusted sensitivity analyses.

15. Safety Analyses

All safety analyses will be conducted using the Safety population.

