15.1 Adverse Events

An AE is defined as any untoward medical occurrence associated with the use of a drug in humans, whether or not considered drug-related. An AE can therefore be any unfavorable and unintended sign (eg, an abnormal laboratory finding), symptom, or disease occurring after the subject started dosing with the study drug, without any judgment about causality. Any pre-existing medical condition that worsens after administration of the study drug will also be considered a new AE. Study drug includes the investigational drug under evaluation and placebo. All AEs will be coded using MedDRA Version 20.1.

Treatment-emergent adverse events (TEAEs) are defined as any AE that occurs or worsens after the first dose of study treatment. AEs recorded in the eCRF which began prior to treatment will not be included in the summary tables but will be included in the AE data listings.

An overall summary will be presented that includes the number of AEs, TEAEs, serious AEs (SAE), and serious TEAEs (TE-SAE). The summary will also include the number and percentage of subjects withdrawn due to an AE, the number and percentage of subjects with an AE resulting in death, and the number and percentage of subjects who experienced at least one AE, TEAE, SAE and TE-SAE, by treatment group and for all subjects. This summary will include breakdowns of AEs further categorized as ocular or non-ocular.

Additional summaries of TEAEs will be provided showing the number and percentage of subjects who experienced at least one TEAE. These summaries will be presented by SOC and PT. Non-ocular TEAEs will be summarized using discrete summary statistics and presented by treatment group at the subject and event level by SOC and PT. Ocular TEAEs will be similarly summarized at the subject and event level as well as for study and fellow eyes separately. If a subject reports the same PT multiple times within the same SOC, that PT will only be reported once within that SOC. As with the PT, if a subject reports multiple conditions within the same SOC, that SOC will only be reported once. In the summary, SOC will be listed in order of descending frequency for all subjects; PTs will be listed in order of descending frequency for all subjects within each SOC. The occurrence of non-ocular and ocular TEAEs will also be tabulated by SOC, PT, and maximal severity.

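### Visit 2 pupil (and, where done, intranasal) summaries pool subjects dosed that day with subjects who did not meet the dosing trigger, which shrinks any acute second-dose effect

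*SAP*

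**What the plan says.** Population. The opening of SAP section 15 says: "All safety analyses will be conducted using the Safety population". SAP 8.3 defines that population: "The Safety population includes all randomized subjects who have received at least one dose of the investigational product". A dose at Visit 1 meets the definition, whatever happens at Visit 2.

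Dosing at Visit 2. SAP 14.1.2 makes the dose conditional: "Treatment with study drug will be administered upon the participant reporting an Ocular Discomfort" "score ≥ 3 at two or more consecutive timepoints in at least one eye during CAE® exposure". A stricter rule applies to an eye already rated 3 at time 0. Protocol 8.3.1 has the same condition: "Treatment with Investigational drug/placebo will be administered upon participant reporting an Ocular Discomfort score". For a participant who does not qualify, SAP 14.1.2 says that "for study drug administration, the timepoint of qualification and the pre-treatment and post-treatment EDS will be missing". SAP section 15 has no parallel rule for safety data.

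Visit 2 examinations. The schedule in SAP 4.2 marks pupil diameter and the intranasal examination after the CAE without reference to dosing. SAP 15.5 gives the pupil timing: "Pupil diameter will be measured in mm pre- and post-treatment at Visit 1 and post-CAE® at Visit 2". It then summarizes observed values and changes from baseline by visit and arm. SAP 15.4 summarizes intranasal results by arm among subjects with a result. Visual acuity and slit-lamp examination at Visit 2 are left to the investigator's discretion (SAP 15.2 and 15.3).

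Exposure. SAP 13.1 sets the expected volume at 400 µL for completers, tabulates percent exposure at or below 80% against above 80%, and provides a listing.

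**The concern.** The plan recognizes that some Visit 2 attendees may not be dosed, and it keeps them out of the primary EDS comparison by setting their values to missing. At the same visit, the safety summaries keep them under their assigned arm. An undosed subject in an active arm contributes a post-CAE pupil diameter, or a nasal finding, to that arm's Visit 2 column, although the last exposure was about two weeks earlier.

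Visit 2 is the only repeat exposure in the trial, and safety is part of the stated objective. SAP section 18 records that pupil diameter was deliberately added as a safety endpoint. Pooling undosed with dosed subjects pulls an acute second-dose difference toward zero, which for a safety measure is the falsely reassuring direction. A reader of the table could not tell a weak effect from a stronger one seen only in those dosed.

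**Working it through.** **The plan's own figure.** Protocol 10.3 expects 40 per arm with 5% dropout: 40 × (1 − 0.05) = 38 completers per arm, and 4 × 40 = 160 randomized. Both reproduce. SAP section 10 defines a completer as someone not discontinued, so an attendee who never meets the trigger is among the 38.

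**Time since last dose in an undosed attendee.** Visit 2 is Day 15 with a window of +4: 15 − 1 = 14 days, up to 19 − 1 = 18 days.

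**Effect of pooling on pupil diameter.** Let
- q = share of subjects with a Visit 2 pupil result who were dosed at Visit 2 (not given in the documents; assumed);
- δ = acute active-minus-placebo effect in dosed subjects;
- m1, m0 = mean change without drug effect in those who meet the trigger and those who do not.

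Assume that undosed subjects carry no drug effect at Visit 2 and that q is the same in both arms.

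Active mean = q(m1 + δ) + (1 − q)m0
Placebo mean = q·m1 + (1 − q)m0
Difference = q·δ

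If the shares differ (qa active, qp placebo), the difference is qa·δ + (qa − qp)(m1 − m0). The second term can have either sign.

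**Range, with 38 attendees per arm.** The last two columns show what a dosed-only summary costs in precision: interval width relative to 38 subjects, √(38/n), and the one-sided 95% upper bound when no event is seen, 1 − 0.05^(1/n).

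| q (assumed) | dosed per arm, n = 38q rounded | share of δ shown when pooled | relative interval width, dosed only | zero-event bound, dosed only |
|---|---|---|---|---|
| 1.0 | 38 | 100% | 1.00 | 7.6% |
| 0.9 | 34 | 90% | 1.06 | 8.4% |
| 0.8 | 30 | 80% | 1.13 | 9.5% |
| 0.7 | 27 | 70% | 1.19 | 10.5% |

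**Time from dose to examination among the dosed.** The trigger needs two consecutive ratings five minutes apart, so a dose can precede the end of the 120-minute exposure by at most about 120 − 5 = 115 minutes, or come close to the end. The interval from CAE exit to examination is not stated, so no lower limit can be given.

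**What exposure data would show.** A completer given a full dose at Visit 1 and none at Visit 2 has 200/400 = 50% exposure and falls in the row at or below 80%. That row could also hold other under-dosed subjects. The instillation and exposure listings (16.2.5.1 and 16.2.5.2) would identify the individuals, and listings 16.2.8.3 and 16.2.8.4 hold their nasal and pupil results. No planned table joins the two.

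**The case against.** Several counter-arguments have force.

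- *The share is unknown and may be near 1.* Most eligibility criteria are redacted, so how strongly entry selects people likely to meet the trigger cannot be judged. Protocol 5.1 and 7.1.2 state dosing at both visits, and SAP 13.1 expects two doses from completers. This stands as a limit on size. It does not remove the gap, because SAP 14.1.2 provides for subjects who do not qualify.
- *The information is already available.* Undosed subjects can be found through the exposure outputs. This is true, but the reader would have to rebuild the summary from listings.
- *Safety summaries are descriptive, and an undosed attendee is still a treated subject.* This stands. No planned test is affected, and a late nasal finding after the first dose is legitimate safety data. It is a reason to keep the overall summaries.
- *A dosed-only summary conditions on an event after randomization.* It does, but the trigger is met before the second dose, so selection does not depend on that dose's effect. Comparability between arms could suffer if the first dose still affects discomfort two weeks later.

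A reader might also infer that the adverse event tables are diluted. The documents do not support that: SAP 15.1 counts events "defined as any AE that occurs or worsens after the first dose of study treatment", cumulatively and not by visit, and a subject not re-dosed has been exposed. Nor does the multiplication by q carry over to every examination. Visit 2 visual acuity and slit-lamp examinations are discretionary, and SAP 15.4 calls the intranasal examination as-needed although the schedule marks it for all. Selective examination could bias those results either way.

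**Conclusion.** The point holds for Visit 2 pupil diameter, and in direction for intranasal results if all attendees are examined. The planned summaries mix subjects dosed that day with attendees last dosed 14 to 18 days earlier, and no safety table separates them. For pupil diameter, the pooled difference is the acute second-dose effect times the share dosed. An assumed 90%, 80% or 70% retains 90%, 80% or 70% of it.

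This rests on three assumptions: some attendees are not dosed; those subjects carry no drug effect at Visit 2; and the share dosed is similar across arms. The documents give no rate, so the size cannot be fixed, and if every attendee is dosed the problem disappears. It is a gap in descriptive reporting that is worth closing. It does not invalidate the safety analysis, and the treatment-emergent definition is not at fault.

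**What to change.** Before unmasking, amend the SAP as follows.

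- **15.4 and 15.5:** keep the overall Visit 2 summary. Add one for Safety subjects dosed at Visit 2, show undosed attendees in a separate column, and give the number dosed per arm.
- **15.2 and 15.3:** do the same where the discretionary examination was performed, and state how many were examined.
- **Listings:** add the time from Visit 2 dose to each examination. The documents do not say that examination times are recorded; if they are not, give the time from dose to CAE exit, if known, and label it as such.
- **15.1:** a summary of treatment-emergent events before and after the Visit 2 dose is optional.
- **Reconcile:** Protocol 5.1 and 7.1.2, which state Visit 2 dosing without condition, with the conditional rule in Protocol 8.3.1; and the as-needed wording of SAP 15.4 with the SAP 4.2 schedule.

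The cost is SAP text and a few columns. Volume given at each visit is already needed for SAP 13.1, and the qualification timepoint is already a covariate in SAP 14.1.2. The downside is precision: at an assumed 80% dosed, intervals are about 13% wider and the zero-event bound rises from 7.6% to 9.5%.

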16.1 Urine Pregnancy Test

The urine pregnancy test will be performed pre-treatment at Visit 1 and at Visit 2. A subject listing of urine pregnancy test results will be produced based on female subjects only.

17. Interim Analyses

There will be no interim analyses in this study.

18. Changes from Protocol-Stated Analyses

The [REDACTED] analysis of the EDS primary endpoint has been revised from a repeated measures [REDACTED] analysis to the analysis described herein. The [REDACTED] analyses of EDS and ocular discomfort during CAE® have been revised to include timepoint of qualification as a covariate. Analysis of pupil diameter as a safety endpoint has been added.

19. Revision History

Documentation of revision to the SAP will commence after approval of the Final version 1.0.

20. Tables

Tables that will be included in the topline delivery are shown in boldface font.

Table Number	Title	Population
TABLE 14.1.1	SUBJECT DISPOSITION	ALL RANDOMIZED SUBJECTS
TABLE 14.1.2.1	DEMOGRAPHICS	ITT
TABLE 14.1.2.2	DEMOGRAPHICS	SAFETY
TABLE 14.1.3.1	BASELINE DISEASE CHARACTERISTICS (STUDY EYE)	ITT
TABLE 14.1.3.2	OCULAR MEDICAL HISTORY	ITT
TABLE 14.1.3.3	NON-OCULAR MEDICAL HISTORY	ITT

Table Number	Title	Population
TABLE 14.1.4.1	CONCOMITANT OCULAR MEDICATIONS BY TREATMENT GROUP, DRUG CLASS AND PREFERRED NAME	ITT
TABLE 14.1.4.2	CONCOMITANT NON-OCULAR MEDICATIONS BY TREATMENT GROUP, DRUG CLASS AND PREFERRED NAME	ITT
TABLE 14.2.1.1	SCHIRMER'S TEST IN STUDY EYE	ITT WITH ODO
TABLE 14.2.1.2	SCHIRMER'S TEST IN STUDY EYE	ITT WITH MCMC
TABLE 14.2.1.3	SCHIRMER'S TEST IN STUDY EYE	PP WITH ODO
TABLE 14.2.1.4	SCHIRMER'S TEST IN STUDY EYE BY SITE	ITT WITH ODO
TABLE 14.2.1.5	SCHIRMER'S TEST IN STUDY EYE TIPPING POINT ANALYSIS	ITT WITH MCMC
TABLE 14.2.1.6	SCHIRMER'S TEST IN STUDY EYE	ITT WITH PMM
TABLE 14.2.1.7	SCHIRMER'S TEST IN STUDY EYE, INFERIOR CORNEAL STAINING SCORE < 1.5	ITT WITH ODO
TABLE 14.2.1.8	SCHIRMER'S TEST IN STUDY EYE, INFERIOR CORNEAL STAINING SCORE >= 1.5	ITT WITH ODO
TABLE 14.2.1.9	SCHIRMER'S TEST IN STUDY EYE, BASELINE EYE DRYNESS SCORE < 60	ITT WITH ODO
TABLE 14.2.1.10	SCHIRMER'S TEST IN STUDY EYE, BASELINE EYE DRYNESS SCORE >= 60	ITT WITH ODO
TABLE 14.2.1.11	SCHIRMER'S TEST IN FELLOW EYE	ITT WITH ODO
TABLE 14.2.1.12	SCHIRMER'S TEST IN FELLOW EYE	PP WITH ODO
TABLE 14.2.1.13	SCHIRMER'S TEST IN FELLOW EYE, INFERIOR CORNEAL STAINING SCORE < 1.5	ITT WITH ODO
TABLE 14.2.1.14	SCHIRMER'S TEST IN FELLOW EYE, INFERIOR CORNEAL STAINING SCORE >= 1.5	ITT WITH ODO

[figure not shown]
Table Number	Title	Population
TABLE 14.2.1.15	SCHIRMER'S TEST IN FELLOW EYE, BASELINE EYE DRYNESS SCORE < 60	ITT WITH ODO
TABLE 14.2.1.16	SCHIRMER'S TEST IN FELLOW EYE, BASELINE EYE DRYNESS SCORE >= 60	ITT WITH ODO
TABLE 14.2.2.1	EYE DRYNESS SCORE ONE-TIMEPOINT ANALYSIS	ITT WITH ODO
TABLE 14.2.2.2	EYE DRYNESS SCORE ONE-TIMEPOINT ANALYSIS	ITT WITH MCMC
TABLE 14.2.2.3	EYE DRYNESS SCORE ONE-TIMEPOINT ANALYSIS	PP WITH ODO
TABLE 14.2.2.4	EYE DRYNESS SCORE ONE-TIMEPOINT ANALYSIS BY SITE	ITT WITH ODO
TABLE 14.2.2.5	EYE DRYNESS SCORE ONE-TIMEPOINT ANALYSIS TIPPING POINT ANALYSIS	ITT WITH MCMC
TABLE 14.2.2.6	EYE DRYNESS SCORE ONE-TIMEPOINT ANALYSIS	ITT WITH PMM
TABLE 14.2.3.1	EYE DRYNESS SCORE DURING CAE BY TIMEPOINT	ITT WITH ODO
TABLE 14.2.3.2	EYE DRYNESS SCORE DURING CAE BY TIMEPOINT	PP WITH ODO
TABLE 14.2.3.3	EYE DRYNESS SCORE POST-TREATMENT THREE-TIMEPOINT ANALYSIS	ITT WITH ODO
TABLE 14.2.3.4	EYE DRYNESS SCORE POST-TREATMENT THREE-TIMEPOINT ANALYSIS	PP WITH ODO
TABLE 14.2.3.5	EYE DRYNESS SCORE DURING CAE MMRM ANALYSIS	ITT WITH ODO
TABLE 14.2.3.6	EYE DRYNESS SCORE DURING CAE MMRM ANALYSIS	PP WITH ODO
TABLE 14.2.3.7	OCULAR DISCOMFORT ([REDACTED] SCALE) DURING CAE BY TIMEPOINT	ITT WITH ODO
TABLE 14.2.3.8	OCULAR DISCOMFORT ([REDACTED] SCALE) DURING CAE BY TIMEPOINT	PP WITH ODO
TABLE 14.3.1.1	ADVERSE EVENT SUMMARY	SAFETY
TABLE 14.3.1.2	ALL OCULAR ADVERSE EVENTS	SAFETY
TABLE 14.3.1.3	ALL NON-OCULAR ADVERSE EVENTS	SAFETY

Table Number	Title	Population
TABLE 14.3.1.4	ALL OCULAR TREATMENT-EMERGENT ADVERSE EVENTS	SAFETY
TABLE 14.3.1.5	ALL NON-OCULAR TREATMENT-EMERGENT ADVERSE EVENTS	SAFETY
TABLE 14.3.1.6	ALL OCULAR TREATMENT-RELATED TREATMENT-EMERGENT ADVERSE EVENTS	SAFETY
TABLE 14.3.1.7	ALL NON-OCULAR TREATMENT-RELATED TREATMENT-EMERGENT ADVERSE EVENTS	SAFETY
TABLE 14.3.1.8	ALL SERIOUS ADVERSE EVENTS	SAFETY
TABLE 14.3.1.9	ALL SERIOUS TREATMENT-RELATED TREATMENT-EMERGENT ADVERSE EVENTS	SAFETY
TABLE 14.3.1.10	ALL OCULAR TREATMENT-EMERGENT ADVERSE EVENTS BY MAXIMAL SEVERITY	SAFETY
TABLE 14.3.1.11	ALL NON-OCULAR TREATMENT-EMERGENT ADVERSE EVENTS BY MAXIMAL SEVERITY	SAFETY
TABLE 14.3.2	BEST-CORRECTED VISUAL ACUITY - LOGMAR	SAFETY
TABLE 14.3.3.1	SLIT LAMP BIOMICROSCOPY	SAFETY
TABLE 14.3.3.2	SHIFT IN SLIT LAMP BIOMICROSCOPY	SAFETY
TABLE 14.3.4.1	INTRANASAL EXAMINATION	SAFETY
TABLE 14.3.4.2	SHIFT IN INTRANASAL EXAMINATION	SAFETY
TABLE 14.3.5	PUPIL DIAMETER (MM)	SAFETY
TABLE 14.3.6	EXPOSURE TO STUDY DRUG	SAFETY

21. Listings

Listing Number	Title
LISTING 16.1.7	RANDOMIZATION SCHEDULE

Listing Number	Title
LISTING 16.2.1	SUBJECT DISPOSITION
LISTING 16.2.2	PROTOCOL DEVIATIONS
LISTING 16.2.3	STUDY POPULATION INCLUSION
LISTING 16.2.4.1	DEMOGRAPHICS
LISTING 16.2.4.2	OCULAR MEDICAL HISTORY
LISTING 16.2.4.3	NON-OCULAR MEDICAL HISTORY
LISTING 16.2.4.4	PRIOR AND CONCOMITANT OCULAR MEDICATIONS
LISTING 16.2.4.5	PRIOR AND CONCOMITANT NON-OCULAR MEDICATIONS
LISTING 16.2.5.1	IN-OFFICE STUDY MEDICATION INSTILLATION
LISTING 16.2.5.2	STUDY DRUG EXPOSURE
LISTING 16.2.5.3	URINE PREGNANCY TEST
LISTING 16.2.6.1	SCHIRMER'S TEST
LISTING 16.2.6.2	EYE DRYNESS SCORE
LISTING 16.2.6.3	EYE DRYNESS SCORE (DURING CAE)
LISTING 16.2.6.4	 OCULAR DISCOMFORT SCALE
LISTING 16.2.6.5	 OCULAR DISCOMFORT SCALE (DURING CAE)
LISTING 16.2.6.6	OCULAR SURFACE DISEASE INDEX (OSDI)
LISTING 16.2.6.7	CORNEAL FLUORESCEIN STAINING (NEI SCALE)
LISTING 16.2.7.1	ALL ADVERSE EVENTS
LISTING 16.2.7.2	SERIOUS ADVERSE EVENTS
LISTING 16.2.7.3	ADVERSE EVENTS LEADING TO TREATMENT DISCONTINUATION
LISTING 16.2.7.4	ADVERSE EVENTS LEADING TO DEATH
LISTING 16.2.8.1	VISUAL ACUITY
LISTING 16.2.8.2	SLIT LAMP BIOMICROSCOPY

Listing Number	Title
LISTING 16.2.8.3	INTRANASAL EXAMINATION
LISTING 16.2.8.4	PUPIL DIAMETER

22. Figures

Figure Number	Title	Population
FIGURE 14.2.1.1	PRE- TO POST-TREATMENT CHANGE IN SCHIRMER'S TEST BY TREATMENT GROUP	ITT WITH ODO
FIGURE 14.2.1.2	PRE- TO 1 MINUTE POST-TREATMENT CHANGE IN EDS BY TREATMENT GROUP	ITT WITH ODO
FIGURE 14.2.2.1	PRE- TO POST-TREATMENT CHANGE IN EDS DURING CAE BY TIMEPOINT AND TREATMENT GROUP	ITT WITH ODO
FIGURE 14.2.2.2	PRE- TO POST-TREATMENT THREE TIMEPOINT AVERAGE CHANGE IN EDS BY TREATMENT GROUP	ITT WITH ODO
FIGURE 14.2.2.3	PRE- TO POST-TREATMENT CHANGE IN EDS DURING CAE BY DURATION AND TREATMENT GROUP, MMRM ANALYSIS	ITT WITH ODO
FIGURE 14.2.2.4	PRE- TO POST-TREATMENT CHANGE IN OCULAR DISCOMFORT ([REDACTED] SCALE) DURING CAE BY TIMEPOINT AND TREATMENT GROUP	ITT WITH ODO
